- Hemoglobin \geq 11.0 g/dL for African American subjects; Hemoglobin \geq 11.5 for non-African American subjects
- Normal screening labs (with exception of the expected hormonal abnormalities inherent in hyperandrogenemia)
- Sexually active subjects must agree to abstain or use double barrier contraception during the study
- Subjects must agree not to take any other medications during the course of the study without approval by the study investigators.

2. List the criteria for exclusion

- Abnormal screening labs (with the exception of the expected hormonal abnormalities inherent in hyperandrogenemia)
- Creatinine clearance less than 90 ml/min as calculated by Cockcroft-Gault equation
- Hemoglobin <11.5 g/dL for non-African American subjects; Hemoglobin < 11.0 g/dL for African American subjects
- Abnormal liver function tests (including AST, ALT, Bilirubin, Albumin, and Alkaline Phosphatase)
- Weight < 34 kg
- History of renal dysfunction, liver dysfunction, congestive heart failure, deep venous thrombosis, breast cancer, endometrial cancer, or cervical cancer
- Pregnant or breast feeding
- On medications known to affect the reproductive axis within 3 months of the study (including oral contraceptive pills, metformin, and spironolactone)
- Are currently participating in another study or have been in one in the last 30 days.
- Subjects using restricted medication (see restrictions below) are excluded unless the subject's primary care provider approves stopping the medication.

3. List any restrictions on use of other drugs or treatments.

Subjects must not take medications known to affect the reproductive axis (including oral contraceptives, metformin, and spironolactone) for 90 days prior to and during the study.

Subjects must not take medications that have the potential to increase metformin blood concentration (including cationic drugs such as amiloride, digoxin, morphine, procainamide, quinidine, quinine, ranitidine, triamterene, trimethoprim, vancomycin which are eliminated by renal tubular secretion have the potential for interaction with metformin by competing for common renal tubular transport systems; cimetidine, which increases (by 60%) peak metformin blood concentrations; furosemide which can increase metformin blood concentration without altering metformin renal clearance; and nifedipine, which can increase metformin absorption). Subjects should limit their intake of alcohol.

Statistical Considerations

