After a potential subject is identified, we will arrange for her to come to the CRU or alternate UVA clinical unit for an outpatient consent and screening exam. The goals and procedures of the study will be explained to the potential subject and her parents, and they will be given the opportunity to ask any questions. The potential subject and her parents will be asked to sign the assent and consent forms. A physician will record a medical history and perform a physical exam. Subjects will need to fast for a minimum of 8 hours prior to screening blood draw. Blood will be drawn for screening tests (CBC, Comprehensive metabolic panel, prolactin, LH, FSH, E₁, E₂, P, total T, androstenedione, 17-OHP, DHEA-S, fasting insulin, Insulin-like Growth Factor 1 (IGF-1), glucose, SHBG, TSH, hCG, cholesterol, LDL, HDL, and a number of cytokines and adipokines (including adiponectin, leptin, resistin, PAI-1, IL-1b, IL-6, IL-8, TNF α , MCP-1, HGF and NGF). In the rare event a subject has an elevated 17-OHP on screening, she will be given a repeat 17-OHP. If the value remains elevated, she will be referred to her pediatrician for further testing to rule out congenital adrenal hyperplasia. They will only be able to continue with the study if they have documented normal 17-OHP levels following cortrosyn stimulation. Potential subjects must fall within the normal range on all blood tests to be admitted to the study, except for hyperandrogenemic girls who will be expected to have some abnormal hormone levels. Subjects will be administered 1 month of iron supplementation following screening, provided their screening labs show they are eligible to participate in the study. As soon as screening lab results are available, and subjects are found to be eligible for study participation, subjects weighing ≤ 36 kg will be given 1- 325 mg tablet a day and subjects weighing >36 kg will be given 2- 325 mg tablets a day. The first overnight admission may occur anytime within this 30 day period or after the 30 day period. Subjects will be given the option to pick up this supply of iron in the Clinical Research Unit or have it mailed to them.

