NOTE: Risk of unplanned pregnancy: If a research subject is sexually active and stops using hormonal contraception while failing to use another non-hormonal method of contraception, there is a risk of unplanned pregnancy. (However, subjects will be counseled to use non-hormonal methods of contraception if sexually active.)

NOTE regarding the risk associated with EMLA cream (topical lidocaine and prilocaine, used to alleviate pain): The risks of lidocaine and prilocaine in general may include (frequency not defined) hypotension, angioedema, shock, hyperpigmentation, erythema, itching, rash, burning, urticaria, burning, stinging, edema, bronchospasm, and hypersensitivity reactions. However, in the case of topical lidocaine/prilocaine use, the non-dermatologic adverse events mentioned above would be extremely unlikely unless large amounts of topical lidocaine/prilocaine were used (allowing significant systemic absorption).

2.2 List by bullet format a summary of safety tests/procedures/observations to be performed.

- Sterile technique will be used.
- Before participation in the studies, all participants will be required to have a normal hemoglobin (≥ 11.5 g/dL for non-African American subjects and ≥ 11.0 g/dL for African American subjects). Hemoglobin levels will be measured prior to every admission. For African American subjects, if the hemoglobin level is < 11.0 , the study will be discontinued. For non-African American subjects, if the hemoglobin level is < 11.5 g/dl, the study will be discontinued.
- Blood loss will be carefully recorded and limited to a maximum of 7cc/kg (10% of estimated total blood volume) in 8 weeks. A total of 467 ml of blood will be drawn during the study (including estimated waste from frequent blood draws), with no more than 243.5 being drawn during any 8 week period. Therefore, girls weighing less than 35 kg will not be able to participate. Iron supplementation (325 mg once or twice a day dependent on weight) will be prescribed to all participants.
- We will warn participants against becoming pregnant during the study. We will require that sexually active subjects use effective double barrier methods of birth control as needed during the study. β -hCG levels will be measured at screening and prior to each admission; if the β -hCG is positive, the study will be discontinued.

2.3 Under what criteria would an INDIVIDUAL SUBJECT'S study treatment or study participation be stopped or modified

At subject, PI or sponsor's request

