An outpatient consenting and screening visit is scheduled for volunteers who express interest in the study. Copies of the approved consent and assent forms are sent to potential subjects beforehand, and we request that the volunteer and her parents review and discuss the forms prior to the screening visit.

The consent and screening visit is held in an outpatient examination room in the CRU or alternate UVA clinical unit. This allows a private conversation between the screening physician and/or study coordinator, the potential

IRB-HSR# 13789: **Effect of Metformin on Sensitivity of the GnRH Pulse Generator to Suppression by Estradiol and Progesterone in Hyperandrogenic Adolescent Girls**

participant, and at least one of her parents (other individuals such as family members are allowed in the room if desired by the potential participant). The screening visit usually occurs in the morning, although rarely it will occur in the afternoon. The aims, procedures, and potential risks of the study are first explained by the study physician. Importantly, the potential participant and her parents are given an opportunity to ask any questions, and concerns are addressed. In cases where the potential participant wants to begin the study and her parents concur, the participant, parents, and physician and/or study coordinator sign the consent form. In cases where only one parent is able to come to the screening visit, we allow the second parent to sign the form in advance of the visit. This is done in conjunction with a conversation during which we offer that parent an opportunity to ask any questions and confirm that they understand the study and are willing for their daughter to participate. We routinely inform potential participants verbally that signing the consent form does not compel them to continue participation in the study. The remainder of the outpatient screening visit (i.e., history, physical, screening blood tests) occurs immediately thereafter. Participants generally begin the main part of the study within 1-2 months of the screening visit.

6. Will subjects sign a consent form for any part of the study? Yes.

7. Will the study procedures be started the same day the subject is recruited for the study? Yes.

► IF YES, explain in detail why the subject cannot be given more time to make a decision to consent.

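### The 30-day gap after another study is shorter than the 8-week blood-loss window, so research blood drawn 31 to 56 days earlier goes uncounted and the cap can be exceeded in a lighter girl

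*Combined protocol and SAP*

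**What the plan says.** Three parts of the protocol bear on this.

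- **Gap from other research.** Inclusion/Exclusion Criteria, item 2, excludes girls who "Are currently participating in another study or have been in one in the last 30 days". It does not say whether the 30 days run back from consent, screening or Admission #1. The same list excludes girls weighing under 34 kg.
- **Blood-loss cap.** Data and Safety Monitoring Plan, item 2.2: "Blood loss will be carefully recorded and limited to a maximum of 7cc/kg (10% of estimated total blood volume) in 8 weeks". The same bullet gives this study's volumes: "A total of 467 ml of blood will be drawn during the study", "with no more than 243.5 being drawn during any 8 week period". From the cap and the 8-week figure it concludes: "Therefore, girls weighing less than 35 kg will not be able to participate".
- **Timing of the first admission.** Outpatient Consent and Screening starts a month of iron once eligibility is known and adds: "The first overnight admission may occur anytime within this 30 day period or after the 30 day period". Appendix: Recruitment, item 5, describes the usual course: "Participants generally begin the main part of the study within 1-2 months of the screening visit".

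No section says that blood drawn in another study is asked about, recorded or counted toward the cap.

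**The concern.** A weight floor obtained by dividing this study's peak volume by the cap protects the cap only if this study's blood is the only research blood in the window. The window is 56 days and the required gap from another study is 30, so 56 - 30 = 26 days of possible earlier sampling are covered by neither the entry rule nor the floor.

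The route is open on paper. The Background names other ongoing studies by the group (IRB-HSR# 8588 and 12160), and the Payment section refers to past and current studies in the same population. The 3-month medication exclusion keeps out girls recently given hormones, but not girls who were only sampled. Light girls are expected: entry starts at age 10, and the iron dosing has a tier at 36 kg or less.

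What is at stake is a limit the protocol sets for itself in minors. A girl could meet every listed entry criterion and exceed that limit, with nothing in the text prompting anyone to look.

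**Working it through.** **Inputs.** From item 2.2: cap 7 mL/kg per 8 weeks (56 days); peak draw 243.5 mL in any 8 weeks (unit taken from the 467 ml total); floor 35 kg. From the exclusion list: gap 30 days; floor 34 kg. From the visit schedule: Admission #2 ends on Day 8, counting Admission #1 as Day 0. Not given: the volume X drawn in the other study inside the shared window.

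**1. The protocol's own floor.** Minimum weight = peak / cap = 243.5 / 7 = 34.8 kg, rounded up to 35 kg. The stated figure reproduces.

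**2. Room under the cap with no earlier study.** Room = 7 × weight - 243.5.

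| Weight (kg) | Cap (mL) | Room (mL) |
|---|---|---|
| 34 | 238 | -5.5 |
| 35 | 245 | 1.5 |
| 40 | 280 | 36.5 |
| 50 | 350 | 106.5 |
| 60 | 420 | 176.5 |

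At 34 kg, which the exclusion list admits, the stated peak exceeds the cap on this study's blood alone. The two floors conflict whatever happens in other studies.

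**3. When earlier blood shares the window.** Let s be the days from screening to Admission #1.

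- If the 30 days run back from screening, a draw just outside the gap lies 30 + s + 8 days before the end of Admission #2. This is within 56 when s is under about 18 (30 + 18 + 8 = 56).
- If they run back from Admission #1, the span is 30 + 8 = 38 days, inside 56 whatever the value of s.

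**4. Weight at which the cap still holds.** Minimum weight = (243.5 + X) / 7. X is an assumption.

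| X (mL) | Minimum weight (kg) |
|---|---|
| 0 | 34.8 |
| 1.5 | 35.0 |
| 10 | 36.2 |
| 50 | 41.9 |
| 100 | 49.1 |

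For scale only, one Admission #1-type visit here draws about 85.75 to 90.25 mL before waste: 61 or 67 samples of 0.75 mL, depending on whether the two-hourly samples replace small ones, plus 7 × 2.5 mL two-hourly, 5 mL at 6 AM and 7 × 2.5 mL for the glucose tolerance test. So 50 to 100 mL is about one night of sampling.

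**5. A correction that lowers step 4 slightly.** The Day 42-49 draw falls at least 30 + 42 = 72 days after the earlier blood and cannot share its window. If the 243.5 mL includes that draw, the shared volume is smaller. The draw's volume is not given; it is at most about 20 mL if the remaining 467 - 243.5 = 223.5 mL is the second pair of admissions with their outpatient draws (243.5 - 223.5 = 20). Taking off the full 20 mL gives 273.5 / 7 = 39.1 kg for X = 50, 323.5 / 7 = 46.2 kg for X = 100, and 21.5 mL of room at 35 kg.

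**The case against.** The strongest reply is that the cap binds in its own right. Item 2.2 says blood loss is recorded and limited, and does not confine this to blood drawn here. On that reading a site must obey the cap as well as the 30-day rule, and two windows of different length do not contradict each other. This stands as far as it goes. But the only volume the protocol sets against the cap is its own 243.5 mL, and it gives no step for learning what was drawn elsewhere.

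Timing also favors the protocol. If the 30 days run to screening and Admission #1 follows a month or more later, earlier blood is at least 60 days before Admission #1 and shares no 56-day window with it. Admission #1 is also tied to cycle day and progesterone level. So the overlap is outside the usual course, though permitted; if the 30 days run to Admission #1, this reply falls away.

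Weight helps too. The Background gives subgroup mean BMIs of 33 and 34 kg/m² in the earlier study; at a BMI of 33, 49 kg corresponds to a height of only about 1.22 m. Those are means, and younger girls may be lighter. Hemoglobin checks before each admission may catch anemia, but they do not enforce a volume limit.

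Three stronger readings are tempting and not supported:

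- **That any girl coming from another study would breach the cap.** The breach needs earlier blood in the 31 to 56 day band, an early enough Admission #1, and a weight below (243.5 + X)/7.
- **That girls up to about 70 kg are at risk.** That takes X = 243.5 mL, an earlier study as heavy as this one falling wholly inside the window. No such sampling-only study is described. Study 8588 measured progesterone sensitivity, so its girls were probably given hormones and would be blocked for 3 months; the design and volumes of 12160 are not in the protocol.
- **That a completer would be lost to the hemoglobin stop at Day 3.** No figure in the protocol links the extra volume to a fall below the threshold.

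**Conclusion.** The point holds as a gap between two sections and as a minor one. The weight floor in item 2.2 guarantees the 8-week cap only when no other research blood falls in the window, and the 30-day rule does not ensure that. The cap can be exceeded in a lighter girl admitted within about 18 days of screening if the 30 days run to screening, or at any interval if they run to Admission #1. On assumed earlier volumes of 50 and 100 mL the affected girls weigh less than about 42 and 49 kg, or about 39 and 46 kg if the full 20 mL correction applies. The earlier volume and the existence of a sampling-only feeder study are assumptions, and the number of girls affected cannot be estimated from the protocol; it is probably small.

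The 34 kg versus 35 kg conflict needs none of these assumptions. At the lower figure the stated peak is 5.5 mL over the protocol's own cap.

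**What to change.** Reconcile the exclusion list with item 2.2 so that the other-study window, the 8-week cap and the two weight floors agree:

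- State the date from which the 30 days are counted.
- State in item 2.2 that the existing 8-week cap applies to all research blood, including blood drawn in other studies, and record the date and volume of any such draws at screening.
- Make the two weight floors consistent with each other and with the cap, and list which visits make up the 243.5 mL so that the calculation can be checked.

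No new limit is needed; which weight figure stands is for the investigator and the IRB. The amendment is a few lines. Its cost falls on the few girls coming from another sampling study, who may wait at most about 56 - 30 = 26 days longer.

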1. **Is stratification/randomization involved?** No.

2. **What are the statistical considerations for the protocol?**

Sample Size Calculation. The primary aim will be to compare the change in 11-hour LH pulse frequency between the 1st and the 2nd admissions ($\Delta_{(2-1)}$) to the change in the 11-hour LH pulse frequency between the 3rd and the 4th admissions ($\Delta_{(4-3)}$). To perform the sample size calculation, we assumed that the linear contrast $\Delta_{(4-3)} - \Delta_{(2-1)}$ will follow a normal distribution with standard deviation 1.02 units. Base on the sample size formula for the paired one-sample standard normal z-test, our calculation indicates that if 30 subjects complete the study, we will have at least an 80% chance of detecting a 1.02 unit or greater difference between $\Delta_{(4-3)}$ and $\Delta_{(2-1)}$ with the two sided type I error rate of the statistical test not exceeding 0.05.

Our prior studies indicate that the subject dropout rate in this study population should not exceed 50%, so 60 subjects will be enrolled to insure that we have 30 completers.

Statistical Analysis: The 11-hour LH pulse frequency data from study admissions 1-4, will be analyzed by way of a mixed-effects linear model. The four 11-hour LH pulse frequency measurements; one measurement from each admission, will function as the respond data. The study admission will be treated as a categorical explanatory factor in the analysis, while the mean 11-hour progesterone level from each admission will be treated as a continuous covariate. Hypothesis testing will be conducted by constructing *a priori* defined within-subject linear contrasts of the 11-hour LH pulse frequency measurements. The primary linear contrast will compare the progesterone adjusted change in 11-hour LH pulse frequency between the 1st and the 2nd admissions ($\Delta_{(2-1)}$) to the progesterone adjusted change in the 11-hour LH pulse frequency between the 3rd and the 4th admissions ($\Delta_{(4-3)}$). We will base our decision whether to reject the null hypothesis that $\Delta_{(4-3)} - \Delta_{(2-1)}=0$ on a two-sided $p \leq 0.05$ decision rule. We will used the same decision rule to determine whether $\Delta_{(2-1)}=0$ and $\Delta_{(4-3)}=0$. The SAS PROC-MIX procedure (SAS Institute Inc., Cary NC) will be used to conduct the aforementioned data analysis.

3. **Do you have an adequate sample size, or is your sample size larger than necessary?**

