We calculated that we will need a sample size of 60 subjects in this study in order to achieve a statistical significance with a power of 80% and Type 1 error rate of 0.05. Given the historical screen failure/dropout/withdrawal rate for 8588/JCM010 of 35% and the additional demands of this study secondary to the addition of metformin, we anticipate a screen failure/dropout/withdrawal rate of around 50%. Therefore, we propose enrolling up to 60 girls with the goal of obtaining complete, analyzable data in 30. We believe this sample size is adequate and not excessive.

4. **What is your plan for primary variable analysis?**

The primary linear contrast will compare the progesterone adjusted change in 11-hour LH pulse frequency between the 1st and the 2nd admissions ($\Delta_{(2-1)}$) to the progesterone adjusted change in the 11-hour LH pulse frequency between the 3rd and the 4th admissions ($\Delta_{(4-3)}$).

5. **What is your plan for secondary variable analysis?** Not applicable.

6. **Have you been working with a statistician in designing this protocol?** Yes.

IF YES, what is their name? [name]

Biomedical Research

1. What will be done in this protocol?

All procedures performed in this protocol are being done solely to answer a research question and generate generalizable knowledge.

Outpatient Consent and Screening

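### The stated inputs (SD 1.02, difference 1.02) need 8 completers for 80% power, not 30, so the sample-size justification does not support the planned size

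*Combined protocol and SAP*

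**What the plan says.** Statistical Considerations, item 2 (Sample Size Calculation), defines the primary contrast as the change in 11-hour LH pulse frequency from admission 3 to 4 minus the change from admission 1 to 2. It assumes that this contrast "will follow a normal distribution with standard deviation 1.02 units". The method is given as "Base on the sample size formula for the paired one-sample standard normal z-test". The result is that "if 30 subjects complete the study, we will have at least an 80% chance of detecting a 1.02 unit or greater difference between" the two changes, with the "two sided type I error rate of the statistical test not exceeding 0.05". Item 2 then doubles 30 to 60 for a dropout rate of up to 50%.

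Item 3, which asks whether the sample is adequate or larger than necessary, answers: "We calculated that we will need a sample size of 60 subjects in this study", tying that number to 80% power and a type I error of 0.05. It goes on to describe up to 60 enrolled with complete data in 30, and ends: "We believe this sample size is adequate and not excessive". The Human Participants section gives the same 30 and 60. No source is given for the value 1.02.

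**The concern.** The same number fills both the SD and the detectable difference. A one-SD shift in a paired design is a large standardized effect and needs few subjects, so 30 completers for 80% power looks far too many on the plan's own terms.

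This calculation is the only quantitative basis for the size of a study in girls aged 10 to 17. Each completer has four overnight admissions with blood drawn every 10 minutes, and section 2.2 of the Data and Safety Monitoring Plan puts the total at 467 ml.

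- **If the SD really is 1.02**, the study enrols several times the number its formula requires, and the statement that the size is not excessive is wrong.
- **If the SD is near 2**, the size is about right, but the printed SD is wrong. Anyone calculating from it would conclude that the study can detect about half the effect it really can.

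**Working it through.** **Inputs (Statistical Considerations, item 2):** SD of the contrast σ = 1.02; difference δ = 1.02; two-sided α = 0.05 (z = 1.960); power 80% (z = 0.842); 30 completers; 50% dropout.

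**1. The plan's own figure.** The named formula is n = [σ(z₀.₉₇₅ + z₀.₈₀)/δ]².

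With σ/δ = 1.02/1.02 = 1, n = (1.960 + 0.842)² = 2.8016² = 7.85, so 8 completers. The plan's 30 is not reproduced. A one-sample t calculation gives 10 (power 68% at n = 8 and 80.3% at n = 10).

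**2. What 30 completers give with SD 1.02.**
- Power for 1.02: Φ(δ√n/σ − 1.960) = Φ(5.477 − 1.960) = 99.98% (99.96% by t).
- Difference detectable with 80% power: 2.8016 × 1.02/√30 = 0.522.

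**3. The SD at which 30, 80% and 1.02 agree.** σ = 1.02 × √30/2.8016 = 1.99. As a check, SD 2.0 gives a detectable difference of 2.8016 × 2.0/√30 = 1.023.

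**4. Sensitivity.** The true SD is not known from the documents, so power for a 1.02-unit difference at 30 completers is shown over an assumed range (z-test):

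| SD of contrast | Power |
|---|---|
| 1.02 | 99.98% |
| 1.5 | 96% |
| 2.0 | 80% |
| 2.5 | 61% |
| 3.0 | 46% |

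**5. Other readings that might rescue 30 (SD and difference both 1.02).**

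| Reading | Completers needed |
|---|---|
| One-sided test | 7 |
| 90% / 95% / 99% / 99.9% power | 11 / 13 / 19 / 26 |
| α of 0.05/3 / 0.01 / 0.001 | 11 / 12 / 18 |
| 1.02 is the SD of each change, changes independent (variance × 2) | 16 |
| 1.02 is the SD of one admission, admissions independent (variance × 4, contrast SD 2.04) | 32; power at 30 is 78.2% |
| Two-sample comparison | 16 per arm, 32 in total |

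Only the last two come near 30. Both contradict the text, which assigns 1.02 to the contrast and uses each subject as her own control.

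**6. Dropout step.** 30/(1 − 0.5) = 60, which is correct. So 60 is the enrolment that yields 30 completers, not a number required for power as item 3 words it. From 8 completers the same step gives 8/(1 − 0.5) = 16 enrolled.

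**The case against.** The strongest defence is that item 2 promises "at least an 80% chance of detecting a 1.02 unit or greater difference between" the two changes. Since 99.98% is at least 80%, the sentence is literally true at 30 completers. That stands for the sentence taken alone, but it does not justify the size. The same sentence would be true at 8 or at 300. Item 2 presents 30 under a sample-size formula, and item 3 says the size was calculated as needed for 80% power.

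Second, 60 is not a separate sizing error. All the relevant sections agree on 30 completers from 60 enrolled. This also stands: only the opening sentence of item 3 is wrong, in calling 60 the number needed for power.

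Third, the documents do not show which figure is wrong. The repeated 1.02 may be the detectable difference copied into the SD position, or a single-admission SD labelled as that of the contrast. Either is inference. The second reading contradicts the label and leaves power at 78.2%, short of 80%. A contrast SD of 1.02 would imply 1.02/√4 = 0.51 pulses per admission under equal, independent errors. The documents give no pulse-frequency SD to compare with that, so nothing here rests on it.

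Finally, if the SD is near 2, the stated size, power and detectable difference are all about right and the trial is not oversized. That is true, and it is why the remedy is to reconcile the figures rather than reduce the sample.

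**Conclusion.** The concern holds. The printed SD, difference, α, power and named formula give 8 completers, against 30 in the plan, and no reading consistent with the text gives 30. Either the SD is about 1.99 instead of 1.02, or the 80%-power difference is about 0.52 instead of 1.02, or the power for 1.02 is 99.98% and the size has no stated rationale. The arithmetic needs no assumption beyond the plan's own inputs. Which figure is wrong cannot be settled from the documents. The paragraph is wrong as written and must be corrected, because it is the trial's only justification for its size.

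**What to change.** In item 2, state the SD of the contrast actually used, with its source, and make the rest of the paragraph follow from it:

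- If the SD is about 2.0, say that 30 completers give about 80% power to detect 1.02 units.
- If 1.02 really is the SD of the contrast, restate the difference detectable with 80% power as 0.52 units, or the power for 1.02 as above 99.9%, and justify afresh why 30 completers are needed.
- If 1.02 is the SD of a single admission, label it so, show how the contrast SD is derived, and report the resulting power.

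In item 3, replace the claim that 60 subjects are needed for 80% power with 30 completers, 60 enrolled at 50% attrition. Keep the statement that the size is not excessive only if the corrected figures support it.

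The cost is the wording of two paragraphs. The correction alone adds no subjects and changes neither the endpoint nor the analysis model. The stated SD or detectable effect may look less favourable afterwards.

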If admission is scheduled to occur greater than one month after the most recent hemoglobin (such as that obtained during screening), a hemoglobin will be repeated 2-5 days before the overnight admission. Documentation of hemoglobin ≥ 11.5 g/dL for non-African American subjects and documentation of hemoglobin ≥ 11.0 g/dL for African American subjects in the previous month is required for the frequent sampling protocol. If overnight admission is scheduled to occur greater than 3 months after screening, then the safety labs (complete blood count, comprehensive metabolic panel) will be repeated at this time.

Day 0: Admission #1

Note:

- Admission #1 will occur on Day 7-11 of the cycle in girls who are cycling with some regularity and on day ≥ 7 in those with infrequent cycles (girls with < 10 cycles per year) provided they have a progesterone level of < 1.5 ng/mL within 3 days of their scheduled first admission. If the progesterone level is >1.5 ng/mL within 3 days of the first admission, the first admission will be cancelled.

IRB-HSR# 13789: Effect of Metformin on Sensitivity of the GnRH Pulse Generator to Suppression by Estradiol and Progesterone in Hyperandrogenic Adolescent Girls

- At each overnight admission a urine HCG will be done to rule out pregnancy and must be negative for the study to continue.

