Starting the day of discharge from Admission #2, subjects will begin taking Metformin 500 mg daily.

Day 14: Increase Metformin dose

On Day 14, the dose of Metformin will be increased to 500 mg twice a day. The subjects will be contacted by phone to inquire regarding adverse events related to the metformin and to remind them to increase the dose of the medication.

Day 21: Increase Metformin dose

On Day 21, the dose of Metformin will be increased to 1000 mg in the morning and 500 mg at night. The subjects will be contacted by phone to inquire regarding adverse events related to the metformin and to remind them to increase the dose of the medication.

Day 28: Increase Metformin dose

On Day 28, the dose of Metformin will be increased to 1000 mg twice a day. The subjects will be contacted by phone to inquire regarding adverse events related to the metformin and to remind them to increase the dose of the medication.

Day 42-49: Outpatient blood draw

Girls will come in after an overnight (>8 hour) fast and have blood drawn for testosterone, SHBG, fasting insulin, fasting glucose, and comprehensive metabolic panel.

Day 84: Admission #3

Note: Admission #3 is timed to the subject's cycles, and therefore is unlikely to occur exactly on Day 84. All girls will take at least 11 weeks (77 days) of Metformin and will then come in for admission #3 at the first appropriate time in their cycle, which will be either on Day 7-11 of their cycle or day ≥ 7 in those with infrequent cycles (girls with < 10 periods per year) provided they have a progesterone level of < 1.5 ng/mL within 3 days of their scheduled first admission. If the progesterone level is >1.5 ng/mL within 3 days of the first admission, the admission will be cancelled.

Admission #3 will be identical to Admission #1. Subjects will be instructed to eat a diet including at least 150 gm of carbohydrate a day for the 3 days preceding the admission

IRB-HSR# 13789: **Effect of Metformin on Sensitivity of the GnRH Pulse Generator to Suppression by Estradiol and Progesterone in Hyperandrogenic Adolescent Girls**

Day 85: Begin Estradiol and Progesterone

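### Does the Admission #3 note tie its progesterone check to the wrong visit by naming the first admission?

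*Combined protocol and SAP*

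**What the plan says.** In the protocol's schedule, the note under *Day 84: Admission #3* governs when a girl returns after metformin. It sets a minimum exposure, "All girls will take at least 11 weeks (77 days) of Metformin", and says that girls "will then come in for admission #3 at the first appropriate time in their cycle". That time is Day 7-11 of the cycle, or "day ≥ 7 in those with infrequent cycles (girls with < 10 periods per year"). The second option carries a hormonal condition: "provided they have a progesterone level of < 1.5 ng/mL within 3 days of their scheduled first admission". The cancellation rule follows: "If the progesterone level is >1.5 ng/mL within 3 days of the first admission, the admission will be cancelled". The paragraph after the note adds: "Admission #3 will be identical to Admission #1".

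The note under *Day 0: Admission #1* has the same condition. Its cancellation sentence reads: "If the progesterone level is >1.5 ng/mL within 3 days of the first admission, the first admission will be cancelled".

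**The concern.** The Admission #3 note names the first admission twice, once in the condition and once in the timing part of the cancellation rule. Admission #1 is on Day 0 and Admission #3 is nominally on Day 84, so on the face of the text the progesterone value that decides the later visit would be taken around the earlier one.

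The visit matters. Under *Statistical Considerations*, the primary contrast compares the change from Admission 3 to Admission 4 with the change from Admission 1 to Admission 2. Admission 3 is therefore the baseline of the post-metformin half. A girl admitted with high endogenous progesterone may already have slowed pulses, which would leave less room for suppression by the study hormones. Girls with regular cycles are still held to Day 7-11. Girls with infrequent cycles may enter on any day from Day 7 with no upper limit, so the progesterone condition is their only stated check on cycle phase. No other visit expressly supplies one: at the Day 42-49 draw, girls "have blood drawn for testosterone, SHBG, fasting insulin, fasting glucose, and comprehensive metabolic panel", and progesterone is not listed.

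**Working it through.** No sample size, power or alpha figure depends on this point. The check is a comparison of the two notes, followed by a test of whether the literal reading could operate.

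**1. The two notes side by side**

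- Condition on progesterone: identical in both notes, word for word.
- Cancellation sentence, timing part: identical in both notes, naming the first admission.
- Cancellation sentence, ending: the Admission #1 note cancels the first admission; the Admission #3 note cancels the admission. The word *first* was taken out here and left in the other two places.

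This is the pattern of a copied paragraph that was only partly edited. The one edit that was made shows that the author had the current visit in mind.

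**2. The same kind of leftover elsewhere**

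- Under *Day 87 and Day 89: Outpatient blood draws*, the text still speaks of study days 3 and 5, the labels from the first hormone round.
- In the pharmacy appendices for estradiol and progesterone, item 2 has the drugs dispensed after the first and third admissions, while item 5 places the second course after the second admission.

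Visit labels were not consistently updated for the second round. That supports reading the Admission #3 wording as clerical. These passages also need to be reconciled with each other.

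**3. Whether the literal reading could work**

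The nominal gap is 84 − 0 = 84 days, or 84 / 7 = 12 weeks. Two literal versions are possible.

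- If the three days run only before the visit, the value is the one that already admitted the girl to Admission #1. It says nothing about her cycle phase 12 weeks later.
- If the three days run on both sides, the window is Day −3 to Day 3. It then takes in the Day 3 draw, which measures peak progesterone while she is taking study progesterone. The target mean is printed as 2-8 ng/dL. If ng/mL was meant (an assumption), the target lies above the 1.5 ng/mL limit and the rule would tend to cancel Admission #3 because the study hormone had been taken. As printed, 2-8 ng/dL is 0.02-0.08 ng/mL and would not trigger it.

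Neither version is a usable rule for a visit that the same note says is timed to the girl's cycle at that point. The only coherent reading is a check within three days of Admission #3.

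**4. What would be seen if the check were missed**

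Because Admission #3 repeats Admission #1, progesterone is sampled every two hours overnight. The mean 11-hour value from each admission is a covariate in the mixed model. A raised value would be recorded and would enter the analysis, although it would not prevent the admission.

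**The case for a change.** The best case for a change is that an entry and cancellation rule should stand on its own words. Section 1.4 of the *Data and Safety Monitoring Plan* treats unapproved departures from study procedures as protocol violations, so staff should not have to infer which visit a rule governs. The statement that Admission #3 repeats Admission #1 might be read as covering only what happens during the stay. Covariate adjustment is also no full substitute for keeping out girls in the wrong cycle phase. Nor can the wording be rescued by taking it to mean the first attempt at Admission #3: the protocol does not define it so, and elsewhere uses the first inpatient or overnight admission for the Day 0 visit.

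It stands that the words are wrong and easily corrected. It does not stand that the check is absent. Even if the repeat statement covers only in-stay procedures, the note itself carries the condition, under its own heading and with *the admission* as the thing cancelled. Nothing in the documents suggests that Admission #3 would go ahead unchecked, and the harm described arises only if staff adopt a reading that makes no operational sense.

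**Conclusion.** This is a clerical slip. The intended check is clear from the note, and under that reading the effect is zero: no change to who is admitted, to the primary contrast, to the target of 30 completers or to the model. If staff did not follow the intent, the effect could not be sized from the documents, because they give no expected share of girls with raised progesterone before Admission #3. The conclusion assumes that staff apply the rule to the visit under whose heading it appears. The two notes should be reconciled as an editorial matter, along with the similar leftovers in the Day 87 and Day 89 paragraph and the pharmacy appendices, leaving the thresholds as they are. That tidying changes nothing the trial does or concludes, so it does not amount to a change in the plan.
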